**ii. FOLLOW-UP EVALUATION**

Patients will be assessed at the two to four standard of care post-operative visits up to six months. As part of standard of care, at each visit the patient will be evaluated for any complications including:

- a. superficial: skin irritation, erythema, suture spitting, cellulitis, superficial wound dehiscence, seroma, hematoma, prolonged wound drainage, need for oral antibiotics, post operatively
- b. Deep: periprosthetic infection, arthrotoomy failure, extensor mechanism failure
- c. Other non-closure associated complications

For research purposes only, a clinical image of the scar will be taken and stored in the patients' medical record. Patients will be asked to fill out the patient component of the Patient and Observer Scar Assessment Scale (POSAS), surgeons will complete the observer scale. The POSAS is a validated reliable scar assessment tool used for the evaluation of linear surgical scars taking into account both surgeons and patients' perceptions. This will occur at one of the standard of care post-op appointments between 2-6 weeks after surgery.

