#### *Secondary Endpoints*

1. Record all complications (including needle sticks and glove perforations) and infections related to the wound closure
2. Calculate the cost difference based on supplies, personnel, and OR time between each technique
3. Gather pictures of wound following closure to evaluate the cosmetic result of barbed versus traditional suture in revision total joint arthroplasty using the Patient and Observer Scar Assessment Scale (POSAS)
4. Calculate the number of suture used and length of incision for each technique

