## **3. STUDY DESIGN/METHODOLOGY**

### **3.1. STUDY DESIGN**

This is a prospective, randomized, controlled trial, parallel four-arm design, single-center study to compare barbed versus traditional suture closure in revision total knee and total hip arthroplasty.

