#### Group #2: Barbed suture closure

1. The capsule will be closed with stratafix symmetric PDS Plus
2. Deep fascia will be closed with Stratafix Symmetric PDS Plus (Stratafix symmetric PDS plus, Ethicon; Johnson & Johnson, Somerville, NJ)
3. Subdermal layer with running number 2-0 barbed suture (stratafix symmetric PDS CT-2, Ethicon; Johnson & Johnson, Somerville, NJ)
4. Subcuticular suture with stratafix spiral monocryl plus, Ethicon
5. followed by the use of skin adhesive (Dermabond advanced, Ethicon; Johnson & Johnson).

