### 3.2.2.RANDOMIZATION

Once Revision TJA candidates are successfully screened, patients meeting eligibility criteria will be randomized into either the barbed or conventional closure group. After informed consent is obtained and the screening interview is conducted, the principle investigator/sub- investigator or research assistant will electronically randomize a patient to a study group (barbed or conventional closure group) using the REDCap database (web-based secure database application).The NYU Statistics Department will provide the randomization scheme that will be used within the REDCap database to randomly assign patients to one of the two treatment groups. Each patient who qualifies for entry into the study will be assigned a unique study number in chronological order.

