**c. PRE-OPERATIVE**

Once revision candidates have been identified and consented, patients will be randomized to traditional vs. barbed suture closure via RedCap. Medical records will be reviewed for baseline patient characteristics, preoperative patient data and laboratory values (Table 1). Prior to operation, a clinical image of the patients existing scar will be obtained for research purposes.

**Table 1.** Collected Baseline Patient Characteristics

Baseline Patient Characteristics
Age
Gender
Body mass index (BMI)
Zip code
American Society of Anesthesiologist (ASA) Score
Insurance type
Preoperative complete blood count (CBC), basic metabolic panel (BMP), and hemoglobin A1c (HbA1c)
Presence of diabetes mellitus
Cigarette smoking status
E-Cigarette smoking status
Immunocompromised status
Charlson Comorbidity Index (CCI)
Indication for Revision Arthroplasty

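### Nothing in the readable protocol keeps patients unaware of their suture arm before they rate their own scar, although the planned skin finish would allow masking at small cost

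*Combined protocol and SAP*

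**What the plan says.** The Secondary Endpoints (section 2.3) include scar images taken "to evaluate the cosmetic result of barbed versus traditional suture in revision total joint arthroplasty using the Patient and Observer Scar Assessment Scale (POSAS"). Under section 9.e.ii, Follow-up Evaluation, the scale has two raters. For the first part, "Patients will be asked to fill out the patient component of the Patient and Observer Scar Assessment Scale (POSAS"); for the second, "surgeons will complete the observer scale". On timing: "This will occur at one of the standard of care post-op appointments between 2-6 weeks after surgery".

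Section 3.1 describes a "prospective, randomized, controlled trial, parallel four-arm design, single-center study" and does not mention masking. Under section 3.2.2 an investigator or "research assistant will electronically randomize a patient to a study group (barbed or conventional closure group) using the REDCap database". Section 9.c places this step before surgery: "Once revision candidates have been identified and consented, patients will be randomized to traditional vs. barbed suture closure via RedCap". Neither section says whether the patient learns the result.

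The planned surface finish is the same in every group. For the knee, section 3.2.1.1 gives a 3-0 subcuticular suture and Dermabond Advanced in both groups. For the hip, section 3.2.1.2 ends each list with a subcuticular suture "followed by the use of skin adhesive" (Dermabond Advanced), and the suture table that follows gives size 3-0 in both arms.

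**The concern.** A scar self-rating is open to expectation. A patient who knows which closure was used may score the scar more kindly or more harshly for that reason. The protocol's Risks section gives each method its own list, with local tissue reaction and delayed healing among the barbed risks and suture spitting and local irritation among the conventional ones. An informed patient could therefore lean either way.

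Such a lean follows the randomised arm exactly, so it enters the arm comparison as if it were an effect of the suture. It could produce a cosmetic difference that does not exist, or hide one that does. This matters because the stated purpose in section 2.1 is a shorter closure with no loss of cosmesis, and the patient part of POSAS is part of the evidence for the second half of that statement. Using a different observer in place of the surgeon would leave the patient's rating as it is.

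**Working it through.** **1. Is there a masking step?** Reading section by section:

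| Section | Content relevant to the patient's knowledge of the arm |
|---|---|
| 3.1 Study design | Randomised, controlled, parallel; nothing on masking |
| 3.2.2 Randomization | Done by study staff in REDCap; nothing on withholding the result |
| 9.b Informed consent | Describes the process; nothing on disclosure of the arm |
| 9.c Pre-operative | Randomisation precedes surgery |
| 9.e.ii Follow-up | Patient and surgeon complete POSAS; nothing on masking |
| 12 Statistical analysis | Regression for differences between surgeons and evaluators |

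No step is found.

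**2. Would the regression remove the bias?** Let the patient score be a + (τ + δ)·arm + surgeon term + evaluator term + error, where τ is the suture effect and δ is the shift due to knowing the arm. Both multiply the same arm indicator, so the arm coefficient estimates τ + δ whichever surgeon or evaluator terms are added. It would not.

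**3. The plan's sample size, for the analysable numbers.** Section 12 assumes a difference of 5 minutes, SD 5 minutes, one-sided alpha 0.025 and power 80%.
- Normal approximation: n = 2(1.960 + 0.842)² × (5/5)² = 15.7, so 16 per arm.
- Exact t-test: 16.7, so 17 per arm, with power 80.7%. The plan's 17 is reproduced.
- Recruitment: 34/(1 − 0.15) = 40 per joint, 80 in total. Reproduced.
- Expected analysable at follow-up: 17 per arm in one joint; 17 + 17 = 34 per arm with hips and knees pooled.

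**4. Illustration of size.** The plan gives no POSAS SD and no bias size, so the mean shift between arms is assumed at b = 0.1 to 0.4 SD, with τ = 0. Section 12 sets two-sided 0.05 and an unpaired t-test for secondary endpoints. The rejection rate is P(|T| > t), where T is noncentral t with 2n − 2 degrees of freedom and noncentrality b√(n/2). For example, with n = 34 and b = 0.3, the noncentrality is 0.3 × √17 = 1.237, the critical value on 66 degrees of freedom is 1.997, and the rate is 23.0%.

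| Assumed shift (SD) | 34 per arm, pooled | 17 per arm, one joint |
|---|---|---|
| 0.1 | 6.9% | 5.9% |
| 0.2 | 12.8% | 8.7% |
| 0.3 | 23.0% | 13.6% |
| 0.4 | 36.9% | 20.5% |

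At full recruitment with no loss (40 and 20 per arm), shifts of 0.2, 0.3 and 0.4 SD give 14.3%, 26.3% and 42.4% pooled, and 9.5%, 15.2% and 23.4% in one joint. If only a fraction of patients learn their arm, the mean shift shrinks roughly in proportion.

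**The case against.** The strongest reply is that the harm rests on silence. A reader might infer that patients are told their arm, but no section says so; sections 3.2.2 and 9.c say only when and by whom randomisation is done. Title and consent pages are not in the text available, so a masking statement there cannot be excluded. This stands, and it limits the point to an omission in the readable protocol. It does not dispose of it: the sections where such a procedure would operate are readable and contain none, so disclosure is left to each member of staff and may go unrecorded.

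Second, the bias may be small. Both knee closures are described as routine care, and barbed suture is already used in about 25% of revisions at the institution, which weakens any novelty effect. At 0.1 SD the error rate stays close to 5%. This also stands, which is why the table is illustration only.

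Third, masking would be imperfect and is not free. Staff must withhold the arm, the operative record may be open to the patient, and suture spitting, which the Risks section associates with the conventional method, could reveal the arm in some patients. The claim that masking would cost nothing is therefore not supported; small cost is the most that can be said.

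A reader might also call the patient part half of the cosmetic endpoint. The plan defines no combined score and no weights, so that does not follow. Nor are skin complications simply self-reported: under section 9.e.ii patients are evaluated for them at visits, so the bias cannot be carried over to that endpoint in full.

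**Conclusion.** The point holds as an avoidable omission affecting the patient-rated part of one secondary endpoint. The readable protocol does not keep patients unaware of their arm, the planned surface finish would allow it, and the planned analysis cannot repair the resulting bias afterwards. Its size cannot be derived from the documents. Under assumed shifts of 0.1 to 0.4 SD, the nominal 5% error would lie between 6.9% and 36.9% pooled, and between 5.9% and 20.5% within one joint, at the analysable numbers that the plan expects. These figures assume no true difference, equal arms, an unpaired t-test and a shift aligned with arm.

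It would be wrong to infer that the trial's main result is compromised: patient knowledge does not enter closure time, and no sample size or alpha changes. It would equally be wrong to infer that POSAS has to move to the 90-day visit; the rating at 2-6 weeks can be protected as scheduled.

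**What to change.** In sections 3.1 and 3.2.2, state that patients are masked to suture arm. In the consent process, describe both closures. Do not tell the patient the arm, or write it in patient-facing papers, until the patient POSAS has been completed at the planned 2-6 week visit, unless disclosure is needed for care. At that visit, ask which closure the patient believes was used, and tabulate the answers by arm so that the success of masking can be judged. If masking is not adopted, say openly that patients are unmasked and interpret the patient POSAS accordingly.

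The cost is protocol and consent wording, one added question, and the discipline of withholding the arm. No extra staff are needed, and neither the recruitment goal of 80 nor the measurement of closure time changes. The remaining weakness is that the medical record or suture spitting may unmask some patients; the added question would show how far this happened.

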### Data Collection

After the patient has enrolled in this study, data will be directly collected from the patient and supplemented with electronic medical record (EMR) chart review. Additional data may be extracted from clinical notes. All members of the team will be trained in the reproducibly collection of clinical data. All data will then be input into REDcap. A member of the research team will be present at each patient follow-up to ensure that all necessary data points are collected. In addition, the research team may assist the physician when measuring the patient's functional outcomes.

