### Statistical Analysis

Descriptive statistics will be used to report baseline characteristics as well as primary and secondary outcomes for the barbed suture and conventional cohorts. Outcomes will be compared between barbed suture and conventional closure (control) for the aforementioned baseline, perioperative and postoperative variables. Continuous or ordinal variables will be reported using unpaired t-tests, and all other categorical variables will be analyzed using Fisher's Exact Test. The test for primary endpoint will be one-sided (with the alternative hypothesis "mean closure time for barbed suture minus mean closure time for traditional suture <0") with a significance level of 0.025. Two-sided tests will be performed for baseline characteristics of patients and secondary endpoints with a significance level of 0.05. To further control for surgeon and evaluator variability we will also perform multivariable linear regression for continuous outcomes of interest and logistic regression for the dichotomous outcomes. Pooled and subgroup analysis for hip and knee revisions will be performed

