## **17. ETHICS/CONFLICT OF INTEREST**

The clinical research study will be conducted in accordance with the current IRB-approved clinical protocol; International Conference of Harmonization (ICH) Good Clinical Practice (GCP) Guidelines adopted by the FDA; and relevant policies, requirements, and regulations of the New York University IRB, State of New York, and applicable federal agencies.

None of the principal investigators, co-investigators or study team members should perform, for any personal gain, services to any supplier of goods or services, as employee, consultant, or in any other capacity which promises compensation of any kind, unless the fact of such transaction or contracts are disclosed in good faith, and the board or committee authorizes such a transaction. Similar association by a family member of principal investigators, co-investigators or study team members or by any other close relative may be inappropriate.

This study is undertaken in good faith with Ethicon research support, the company (Ethicon Inc) will provide suture and research support for the completion of this study.

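### Surgeons score the observer POSAS with no masking planned for anyone, so the cosmetic comparison is open to a rating bias that the planned regression cannot remove

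*Combined protocol and SAP*

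**What the plan says.** Section 9.e.ii gives the patient part of POSAS to the patient, and for the other part "surgeons will complete the observer scale". It is scored once: "This will occur at one of the standard of care post-op appointments between 2-6 weeks after surgery". It does not say whether the scoring surgeon is the one who closed the wound.

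The cosmetic result is a secondary endpoint in section 2.3: "Gather pictures of wound following closure to evaluate the cosmetic result of barbed versus traditional suture", using POSAS. Section 2.1 makes it part of the purpose, which is a shorter closure at no cost in scar appearance or wound complications.

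On masking, the design statement in section 3.1 reads "This is a prospective, randomized, controlled trial, parallel four-arm design, single-center study" and goes on to name the comparison. Neither it nor any other section mentions blinding.

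Four other places bear on the point:

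- Section 11, Data Collection: "A member of the research team will be present at each patient follow-up". The stated task is to see that the data are complete.
- Section 3.2.2 lets the investigator, a sub-investigator or a research assistant carry out the randomization in REDCap.
- Section 12 opens the regression plan with "To further control for surgeon and evaluator variability".
- Section 17 says the suture manufacturer "will provide suture and research support for the completion of this study".

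**The concern.** POSAS is a judgement. A surgeon who closed the wound knows which technique was used, and a colleague may know it too. A rater who expects one closure to look better, or who wants to show that it looks no worse, can move the score without intending to. Manufacturer support is not evidence of bias, but it makes an unmasked subjective rating harder to defend.

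The harm can run either way. A shift may create a cosmetic difference that does not exist. It may also cover a real one, which matters more here because the trial hopes to report that cosmesis was not sacrificed.

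The plan recognises rater variability and proposes to adjust for it, but adjustment deals with a different problem. It removes the average difference between lenient and strict raters. It leaves untouched a tendency to score one arm more kindly than the other.

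**Working it through.** **The plan's own figure.** Section 12 sizes the trial on closure time: difference 5 minutes, SD 5 minutes, one-sided alpha 0.025, power 80%. The t-test solution is 16.7, so 17 per group (power 80.7% at 17). That is 34 per joint, and 34 / 0.85 = 40 per joint, 80 in total. The figure reproduces. It says nothing about POSAS, for which the document gives no SD, no target difference and no power.

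**Patients available for POSAS.** POSAS is a follow-up measure, so the planned 15% loss applies: 80 × 0.85 = 68, or 34 per arm pooled and 17 per arm within one joint. With no loss these are 40 and 20.

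**False differences from a rating shift.** Suppose the closures do not differ in appearance, but ratings shift by d standard deviations between arms because the arm is known. The values of d are assumed. The two-sided test at 0.05 (section 12, secondary endpoints) then follows a noncentral t distribution with 2n − 2 degrees of freedom and noncentrality d × √(n/2). For n = 34, √17 = 4.123, so d = 0.2, 0.3 and 0.5 give 0.825, 1.237 and 2.062, against a critical value of 1.997. The chance of a significant result is:

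| Patients per arm | No shift | 0.2 SD | 0.3 SD | 0.5 SD |
|---|---|---|---|---|
| 34 (pooled, after 15% loss) | 5% | 13% | 23% | 53% |
| 40 (pooled, no loss) | 5% | 14% | 26% | 60% |
| 17 (one joint, after 15% loss) | 5% | 9% | 14% | 29% |
| 20 (one joint, no loss) | 5% | 9% | 15% | 34% |

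**A hidden difference.** The same table shows the reverse. If the closures truly differed by 0.5 SD and the shift ran the other way by 0.3 SD, the apparent difference would be 0.5 − 0.3 = 0.2 SD. At 34 per arm the chance of detecting it would fall from 53% to 13%.

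**Why regression does not help.** Write an observer score as: intercept + arm effect + surgeon effect + rater effect + (shift × arm) + error. The arm effect and the shift multiply the same 0/1 variable, so the fitted arm coefficient estimates their sum. Surgeon or rater terms do not change that.

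**Surgeon and evaluator terms.** If every surgeon rates only his or her own patients, the two sets of indicators are identical. With 5 surgeons (assumed), the model has 1 intercept + 1 arm + 4 surgeon + 4 evaluator = 10 columns but rank 6. The arm coefficient can still be estimated. The surgeon and evaluator effects cannot be told apart.

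**The case against.** The strongest reply is that the text says less than a critic may read into it.

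- A reader might infer that the operating surgeon scores his or her own closure. Section 9.e.ii says only surgeons, and section 12 names surgeon and evaluator as two things, which may mean that they can differ. This stands. The plan permits self-scoring and has no safeguard against it, but does not prescribe it. The overlap of the two model terms is likewise conditional, and it does no harm to the arm estimate.
- A reader might infer that an uninvolved rater is already at the visit. The documents do not support that. Section 11 describes someone who checks data capture, trained in data collection but not stated to be trained in scar scoring. Section 3.2.2 allows research staff to randomize, and under section 9.d the number of sutures used goes into REDCap. That person could know the arm, so a usable rater has to be arranged.
- A reader might infer that the comparison is biased. Only the possibility can be shown. The percentages rest wholly on assumed shifts.
- The scope is narrow: the observer part of one secondary endpoint, scored once. Closure time, the sample size and the primary test are unaffected, and the patient part is collected separately. This stands, although patients are not masked either.
- Both arms finish with a subcuticular suture and skin adhesive (section 3.2.1), which suggests that the skin may not betray the arm. That is inference: suture spitting or irritation might reveal it.

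Scar photographs do not close the gap as planned. An image "a clinical image of the scar will be taken and stored in the patients' medical record", but no masked reading of it is described.

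**Conclusion.** The concern holds in a limited form. A subjective secondary endpoint tied to the trial's purpose is scored by surgeons, no one is to be masked, and the planned adjustment cannot correct a shift that follows the arm. The documents establish a risk of bias in the observer scale. They do not establish that bias will occur, or its direction or size.

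The illustrative size, a false-positive rate of about 13% to 53% at 34 per arm instead of 5%, assumes shifts of 0.2 to 0.5 SD, equal arms, the planned 15% loss and a t-test on the observer score. A negligible shift would leave the test at 5%. The case for change rests on the small cost of prevention, since no analysis can repair the scores afterwards.

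**What to change.** In section 9.e.ii, state who completes the observer scale: a trained member of the existing research team, or another participating surgeon, who was not in theatre for that case, did not randomize that patient and is not shown the allocation or suture fields in REDCap. Add that patients are not told their closure type until they have completed the patient scale. Ask the rater to note any case in which the arm became known before scoring.

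In the data collection form, record the evaluator separately from the operating surgeon, so that the regression in section 12 has two distinct variables to use.

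The cost is protocol wording, brief POSAS training, restricted REDCap access for raters, and keeping the randomizing and rating roles apart among existing staff. It needs no extra visit and no change to the sample size or primary analysis. Label: cheap improvement.

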**f. SCHEDULE OF ACTIVITIES**

Study Interval	Preoperative	Peri-operative	Post-Operative
	Screening	Date of Surgery	Follow-up Visits up to 3 months (0-90 days)
Review of demographics and preoperative variables (Table 1)	X		
Measurement of height, weight and BMI	X		
Screening—using eligibility criteria	X		
Patient Consent	X		
Preoperative image of scar	X		
Perioperative Values (Table 2)		X	
Postoperative Variables (Table 2)		X	X

**Table 2.** Collected peri- and post-operative variables

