**Perioperative Variables**

Closure Time Incision Length Number of sutures used will be counted and recorded Any needle sticks or glove perforations Dressing Type Preoperative Incision Clinical Image
Postoperative Variables
Superficial wound complications: Skin irritation, erythema, suture spitting, cellulitis, superficial wound dehiscence, seroma, hematoma, prolonged wound drainage Deep wound complications: periprosthetic infection, arthrotomy failure, extensor mechanism failure Other non-closure associated complications Revision procedures for infection Revision procedures for any reason Post-operative antibiotic therapy Use of chronic antibiotic suppression therapy Post-operative Clinical Image (research only) POSAS Wound Score (research only)

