## 10. STUDY DURATION

This study is designed as a prospective longitudinal study with participants remaining in the study for 3 months following revision total joint arthroplasty. Data collection for each individual study participant will be concluded at the 90-day post-surgical follow-up visit. Duration of the trial is expected to be two years in order to enroll an adequate number of patients and follow outcomes for at least 3 months postoperatively. The entire study is expected to last approximately 24 months.

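### The only cosmetic rating (POSAS) is taken once, at any visit from 2 to 6 weeks, and its analysis ignores time since surgery; a repeat at the existing 90-day visit would be a cheap improvement

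*Combined protocol and SAP*

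**What the plan says.** All references are to the combined protocol and SAP.

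- **Endpoint.** Section 2.3 makes the POSAS, with photographs, the measure of the cosmetic secondary endpoint. It names no assessment time.
- **Timing.** Section 9.e.ii asks patients for the patient scale and surgeons for the observer scale, with a scar image, and adds: "This will occur at one of the standard of care post-op appointments between 2-6 weeks after surgery". This is the only specific timing rule for the POSAS.
- **Schedule.** Section 9.f puts all postoperative variables, the POSAS among them, in a single follow-up column covering days 0 to 90. It gives the POSAS no time point of its own.
- **End of follow-up.** Section 10 states: "Data collection for each individual study participant will be concluded at the 90-day post-surgical follow-up visit". Section 9.e.ii gives a different length: "Patients will be assessed at the two to four standard of care post-operative visits up to six months".
- **Analysis.** Section 12 states: "Continuous or ordinal variables will be reported using unpaired t-tests". It adds multivariable linear regression for continuous outcomes to control for surgeon and evaluator. Time since surgery is not listed as a covariate.

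**The concern.** Section 2.1 describes the aim as faster closure with no loss of cosmesis and no more wound complications. The POSAS is the only cosmetic instrument, so what the trial can say about cosmesis rests on this one rating.

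That rating has two weaknesses. First, patients are scored at wound ages that may differ three-fold. If the score changes as the scar matures, this spread adds variation unrelated to closure method, and a real difference becomes easier to miss. Second, no rating is required after week 6, although the patient is due to be seen at 90 days. The trial would end with no scar assessment at its own last visit.

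**Working it through.** **The plan's own figure.** The documents give no sample size, SD or effect size for the POSAS. The stated size is for closure time: difference 5 minutes, SD 5 minutes, one-sided alpha 0.025, power 80% (section 12). With a standardized difference of 5/5 = 1, the noncentral t-test gives power 78.1% at 16 per group and 80.7% at 17. The stated 17 is therefore reproduced. Two groups make 34 per joint; 34/0.85 = 40 per joint, 80 in total. None of this depends on POSAS timing.

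**Timing, from sections 9.e.ii and 10.**

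- Window: 2 × 7 = day 14 to 6 × 7 = day 42, so 28 days wide, with a ratio of 42/14 = 3.
- Gap to the 90-day visit: 90 − 42 = 48 days at the shortest, 90 − 14 = 76 days at the longest.

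**Spread of wound age (assumption: visits even over the window).** The variance is 4²/12 = 1.33 weeks², and the SD is 28/√12 = 8.1 days. As an extreme case, half the visits at week 2 and half at week 6 gives a variance of 2² = 4 weeks².

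**Loss of precision.** Let the between-patient SD at a fixed wound age be 1, and let the score change by *k* SD per week (assumed). Total variance is 1 + *k*² × Var(wound age).

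| *k* (SD per week) | Even spread | Half at week 2, half at week 6 |
|---|---|---|
| 0.1 | 1 + 0.01 × 1.33 = 1.013 (+1%) | 1 + 0.01 × 4 = 1.04 (+4%) |
| 0.25 | 1 + 0.0625 × 1.33 = 1.083 (+8%) | 1 + 0.0625 × 4 = 1.25 (+25%) |
| 0.5 | 1 + 0.25 × 1.33 = 1.333 (+33%) | 1 + 0.25 × 4 = 2.00 (+100%) |

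**In terms of power.** With 40/2 = 20 per arm within one joint and two-sided alpha 0.05, the difference detectable with 80% power at a fixed wound age is 0.91 SD. Dividing 0.909 by the square root of the total variance and recomputing, power for that difference is 79%, 77% or 68% for *k* = 0.1, 0.25 or 0.5 with even spread. It is 78%, 71% or 51% in the extreme case.

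**Could chance alone make timing differ by arm?** Pooled over joints there are 80/2 = 40 per arm. Under even spread, the standard error of the difference in mean timing is √(2 × 1.33/40) = 0.26 weeks. A one-week difference is 1/0.26, about 3.9 standard errors (two-sided probability about 0.0001). A gap of that size would need a systematic cause.

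**The case against.** The strongest case against is that one early rating at a routine visit is a coherent choice for a single secondary endpoint, perhaps made for completeness. Several parts of that case stand.

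- **Analysis.** The POSAS is not left to a t-test alone, since regression is also planned. What remains is that wound age is missing from it.
- **Later wound events.** Suture spitting, dehiscence and drainage after the rating are not lost. Section 9.e.ii has them evaluated at each visit, and complications are a secondary endpoint in their own right. They simply cannot show in the scar score.
- **Small slopes.** At 0.1 SD per week with even spread the loss is about 1%, which is negligible.
- **The 90-day visit.** No window is stated for it, so moving a rating there does not by itself fix wound age.

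A reader might go further and infer that the cosmetic comparison is biased. If mean timing differed by one week between arms, with 40 per arm and the timing variance included, the false-positive rate would be about 7%, 19% or 48% at 0.1, 0.25 or 0.5 SD per week. Leaving out that variance would put the last figure near 60%, which overstates it. The documents do not support the premise in any case. Allocation is randomized, both arms follow the same routine visits, and nothing describes a mechanism for a shift of that size. The choice of visit is open and no blinding of the scoring surgeon is described, so a timing difference is possible, but it is not shown.

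The objection does not remove the core point: no passage fixes the rating time, adjusts for it, or requires a rating after week 6.

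**Conclusion.** The point holds as a matter of precision and of how late the scar is assessed. The single POSAS mixes wound ages from day 14 to day 42, its planned analysis does not account for this, and it precedes the end of data collection by 48 to 76 days.

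The cost in variance is about 1% to 33% with evenly spread visits, and up to 100% if visits cluster at the two ends of the window. Both ranges rest on assumed rates of 0.1 to 0.5 SD per week, so the loss may be trivial or material. A claim of bias is not supported. Closure time and the sample size of 80 are untouched. This is a cheap improvement to a secondary endpoint, not a flaw in the trial's main comparison.

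**What to change.** 1. Keep the 2 to 6 week rating as the early cosmetic measure. Record days since surgery and add it as a covariate in the POSAS regression already planned. Show its distribution by arm, so that any timing difference is visible.
2. Repeat the POSAS and photograph at the existing 90-day visit, with a stated visit window, and report it as the later cosmetic measure.
3. Give both time points in section 2.3 and in the schedule of activities, and reconcile the follow-up length (six months in section 9.e.ii, 90 days in sections 9.f and 10).

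The cost is one short questionnaire, completed by patient and surgeon, and one photograph. Section 11 already has a research team member present at each follow-up. Days since surgery follows from the surgery and visit dates. The downside is some missing 90-day ratings, but the early rating is kept. No extra patients or visits are needed.
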